#### 3.2.3.4 Randomization and Stratification

After written consent has been obtained, all screening procedures have been completed, and all inclusion/exclusion criteria have been met, the patient will be assigned an allocation number. Once an allocation number is assigned, it cannot be re-assigned to another patient.

In an effort to strive for adequate representation of patients from different weight groups (reflective of patient gestational age) in both treatment arms, randomization will be stratified into 3 weight categories (based on weight at study entry): <1000 grams, 1000 to 1500 grams, and >1500 grams. Patients will be stratified into each of the weight categories in a manner consistent with the 2:1 randomization of caspofungin to amphotericin B deoxycholate.

A single patient/subject cannot be assigned more than 1 allocation number.

# 3.2.3.5 Treatment Evaluation/Follow-Up

# 3.2.3.5.1 Procedures Performed During the Treatment Phase

While on study therapy, the patient will undergo the following procedures (also refer to the Study Therapy Visit on the Study Flow Chart, Section 1.7):

**Protocol/Amendment No.:** 064-02

• Assessment of symptoms and signs of the invasive *Candida* infection: An assessment of symptoms and signs of the *Candida* infection should be performed daily while on study therapy and on the last day of study therapy. These findings should be recorded on the source documents and the appropriate eCRF.

- Vital signs (including weight): Certain vital signs (pulse, respiratory rate, blood pressure, and temperature) should be performed at least once daily while on study therapy and on the last day of study therapy. It is preferred that the method for obtaining temperatures (e.g., oral or tympanic) is consistent throughout the course of study therapy. The most abnormal vital sign findings within the previous 24 hours should be recorded on the appropriate eCRF. Weight should also be collected at least once weekly while on study therapy as a standard procedure when evaluating vital signs and to ensure the appropriate dose of study therapy is being maintained. Weight should also be collected on the day of pharmacokinetic assessment (Day 4 or Day 7). The weekly weight result should also be recorded on the appropriate eCRF.
- Physical examination: A physical examination, including a detailed description of the nature and extent of the invasive *Candida* infection, should be performed on Day 4 and Day 7 of study therapy, twice weekly thereafter (while on study therapy), and on the last day of study therapy. Any abnormal findings should be recorded on the appropriate eCRF.
- Follow-up blood cultures: For patients with candidemia, follow-up blood cultures should be collected periodically while on study therapy until cultures are negative for *Candida* (on at least 2 separate occasions). All results should be recorded on the appropriate eCRF. The general IDSA guidelines for treatment management of candidemia are included in Appendix 6.3.
- Follow-up cultures from non-blood samples: Patients with non-blood sites of invasive candidiasis should have follow-up cultures collected from the non-blood site of *Candida* infection, as clinically indicated by the patient's signs and symptoms of infection and radiographic abnormalities. All results should be recorded on the appropriate eCRF. Specifically, patients with known meningoencephalitis should have follow-up CSF cultures performed on a periodic basis while on study therapy until negative follow-up CSF cultures are documented. The general IDSA guidelines for treatment management of non-fungemic sites of infection are included in Appendix 6.3.
- Follow-up radiographs: Follow-up radiographs should be performed from the site(s) of infection (e.g., echocardiogram, chest/abdominal ultrasound, CT, or MRI) as clinically indicated, based on the site of infection. If a radiographic study that helped confirm the diagnosis of invasive candidiasis is deemed necessary to assess the outcome the outcome of study therapy, the follow-up radiographic study must be obtained within 72 hours (3 days) prior to the completion of study therapy. All results should be recorded on the appropriate eCRF. The general IDSA guidelines for treatment management of the various sites of invasive *Candida* infection are included in Appendix 6.3.

**Protocol/Amendment No.:** 064-02

Study therapy administration: During the study therapy period, the study drug (either caspofungin or amphotericin B deoxycholate) will be prepared by the unblinded pharmacist as outlined in Section 2.4.2 (Treatment Plan). All study therapy (caspofungin or amphotericin B deoxycholate) will be administered intravenously as a single once-daily dose. Each infusion should be administered over approximately 2 hours. The IV line should be flushed thoroughly after each study therapy infusion. Infusion of study therapy may be given through either a pediatric syringe pump or ambulatory pump if this will help ensure that the patient receives the complete dose. As these 2 products differ in color, opaque masking of the infusion materials (e.g., infusion syringe and tubing) will be used to ensure adequate blinding of the treatment group. The unblinded pharmacist will be responsible to cover the infusion materials with opaque masking. Importantly, the unblinded pharmacist will not be involved in any of the postinfusion evaluations for the patient. All study personnel involved with the postinfusion evaluations of safety and efficacy outcomes, including the study coordinator(s), investigator, or subinvestigator(s), must have no access to the treatment group assignment or the preparation of the study infusion. Additional details on study therapy preparation are included in the Pharmacy Binder.

Of note, total parenteral nutrition (TPN) can be administered to patients enrolled in this study. However, it is preferred that TPN is not infused through the same intravenous line as the study therapy. For those patients with catheters containing multiple lumens, study therapy should be administered via a separate lumen than the lumen used for TPN infusion. For patients with single lumen catheters as the only intravenous access site, TPN should be held during the 2-hour infusion of study therapy. In this case, the IV line should be flushed thoroughly prior to and following study therapy infusion.

- Blood for laboratory safety tests: Selected hematology and blood chemistry tests from blood will be performed on Day 4 (± 1 day) and Day 7 of study therapy, twice weekly thereafter (while on study therapy), and on the last day of study therapy. The selected laboratory tests for safety evaluation are outlined in Appendix 6.1. The results, which will be tested locally, should be recorded on the appropriate eCRF.
- Blood (plasma) for pharmacokinetic evaluation: Three blood samples (each 350 μL) should be collected from all patients. Each patient will be randomly assigned to one of 8 sampling schedules; all 3 samples are to be taken on the same study day. Half of the patients will have samples taken on Study Day 4 and the other half will have samples taken on Study Day 7. If it is not possible to take samples on the assigned Study Day, it is recommended that samples be taken on the following Study Day.

Blood samples will be collected from all patients at the time of peak concentration (immediately after the end of study therapy infusion) and time of trough concentration (approximately 24 hours after the start of study therapy infusion but prior to the next day's dose). In addition, a sample will be collected at an intermediate time between peak and trough times as shown in Table 3-4, in Section 3.3.2. Plasma will be separated from blood and sent to a central laboratory for pharmacokinetic testing. The exact time and date of blood sampling should be recorded on the appropriate eCRF.

**Protocol/Amendment No.:** 064-02

Weight should be measured within 12 hours prior to the infusion of study therapy on the assigned day of pharmacokinetic blood sampling, and the study therapy dose given on the pharmacokinetic sample day should be adjusted to reflect the most recently measured weight.

- CSF for pharmacokinetic evaluation: If a patient undergoes any procedure that involves collecting CSF while on study therapy, approximately 350 µL of CSF should be retained for pharmacokinetic assessments. The CSF will also be sent to a central laboratory for pharmacokinetic testing. The exact time and date of CSF sampling should be recorded on the appropriate eCRF.
- Monitoring for adverse experiences: Patient will be monitored daily for adverse experiences while on study therapy. Any findings consistent with an adverse experience should be recorded on the appropriate eCRF. Please refer to Section 3.4 (Safety Measurements) for further details.
- Efficacy evaluation: Resolution or progression of disease should be documented by assessment of symptoms and signs, follow-up culture results, and follow-up radiographic studies, as appropriate. An efficacy evaluation for fungal-free survival will be performed on the last day of study therapy. This evaluation will be recorded on the appropriate eCRF. Please refer to Section 3.3 (Efficacy Measurements) for further details.

# 3.2.3.5.2 Procedures Performed During the Posttherapy Follow-up Visits

At the 2- and 8-week posttherapy follow-up visits, the patient will undergo the following procedures (also refer to the Follow-up Assessment Visit on the Study Flow Chart, Section 1.7):

- Assessment of symptoms and signs for invasive Candida infection: Potential symptoms and signs of the patient's *Candida* infection will be assessed at the 2-week and 8-week posttherapy follow-up visits. Any findings should be recorded on the source documents and the appropriate eCRF.
- Vital signs: Assessments of specific vital signs (pulse, respiratory rate, blood pressure, and temperature) should be performed at the 2-week and 8-week posttherapy follow-up visits. These findings should be recorded on the appropriate eCRF.
- Physical examination: A physical examination, including a detailed description of the nature and extent of the *Candida* infection, should be performed at the 2-week and 8-week posttherapy follow-up visits. Any abnormal findings should be recorded on the appropriate eCRF.
- Follow-up blood or non-blood samples: Patients should have follow-up blood (or pertinent non-blood) cultures collected, as clinically indicated, by the patient's signs and symptoms of infection and radiographic abnormalities through the 8-week posttherapy follow-up visit. All results should be recorded on the appropriate eCRF.
- Follow-up radiographs: Follow-up radiographs should be performed from the site(s) of infection (e.g., echocardiogram, chest/abdominal ultrasound, CT, or MRI) as

**Protocol/Amendment No.:** 064-02

clinically indicated based on the site of infection, through the 8-week posttherapy follow-up visit. All results should be recorded on the appropriate eCRF.

- Blood for laboratory safety tests: Selected hematology and blood chemistry tests from blood will be performed at the 2-week posttherapy follow-up visit. The selected laboratory tests for safety evaluation are outlined in Appendix 6.1. The results, which will be tested locally, should be recorded on the appropriate eCRF.
- Monitoring for adverse experiences: After the completion of study therapy, patient will be monitored for adverse experiences through the 2-week posttherapy follow-up visit. Any findings consistent with an adverse experience should be recorded on the appropriate eCRF. Please refer to Section 3.4 (Safety Measurements) for further details.
- Efficacy evaluation: Resolution or progression of disease should be documented by assessment of symptoms and signs, follow-up culture results, and follow-up radiographic studies, as appropriate. An efficacy evaluation for fungal-free survival will be performed at the 2-week posttherapy follow-up visit. An efficacy evaluation for the development of complicated candidiasis will be performed through the 8-week posttherapy follow-up visit. These evaluations will be recorded on the appropriate eCRFs. Please refer to Section 3.3 (Efficacy Measurements) for further details.

# 3.2.3.6 Blinding/Unblinding

This is a double-blind study in which the patients, the investigator (and site staff, with the exception of the unblinded pharmacists who will not be involved in patient assessment), and members of the SPONSOR staff (or designee) directly involved with the conduct of the study will remain blinded to the treatment administered to all patients.

In the event that an individual patient becomes unblinded to treatment group (either accidental unblinding or emergency unblinding for a serious adverse experience), the investigator must do the following:

- Immediately notify the SPONSOR Clinical Monitor or Clinical Scientist (CS), or respective designees;
- Promptly document the circumstances in the patient's chart;
- Document the unblinding on the Patient Unblinding Log located in the Administrative Binder.

Every effort should be made to contact the Clinical Monitor or CS (or their respective designees) prior to performing an emergency unblinding of any patient.

#### 3.2.3.7 Discontinuation/Withdrawal from Study

Subjects/patients may withdraw at any time or be dropped from the study at the discretion of the investigator should any untoward effects occur. In addition, a subject/patient may be withdrawn by the investigator or the SPONSOR if he/she violates the study plan or for administrative and/or other safety reasons. The investigator or study coordinator must notify the SPONSOR immediately when a subject/patient has been discontinued/ withdrawn due to an adverse experience (telephone or FAX). When a subject/patient

**Protocol/Amendment No.:** 064-02

discontinues/withdraws prior to study completion, all applicable activities scheduled for the final study visit should be performed at the time of discontinuation. Any adverse experiences which are present at the time of discontinuation/withdrawal should be followed in accordance with the safety requirements outlined in Section 3.4 SAFETY MEASUREMENTS - DETAILS.

#### 3.2.3.7.1 Discontinuation/Withdrawal Criteria

Discontinuation from study therapy should be done for the following reason(s):

- The patient's parent (or guardian) refuses further treatment or follow-up and withdraws consent.
- Continuation is not in the best interest of the patient, in the judgment of the investigator.
- Failure to demonstrate or sustain clinical improvement after a course of study therapy. In general, patients who do not have some clinical evidence of improvement by Day 7 of therapy should be discontinued.
- Significant progression of invasive candidiasis after at least 72 hours of study therapy.
- The need to increase the dose of the antifungal study therapy or to give another systemic antifungal drug in addition to the antifungal study therapy.
- Development of signs or symptoms of a rapidly progressive underlying disease that would preclude evaluation of therapy, or that would render continuation in the study inadvisable, in the judgment of the investigator.
- Development of concomitant fungal infection with an organism that is not susceptible to the antifungal study therapy.
- Instances in which pretherapy or follow-up microbiologic studies indicate that the etiologic pathogen(s) of the index infection is/are not susceptible to amphotericin B deoxycholate and/or caspofungin.
- Development of a serious adverse experience related to study therapy or the occurrence of an adverse clinical experience or clinically significant laboratory change or abnormality that, in the judgment of the investigator, warrants withdrawal of the patient from the antifungal study therapy.
- An elevated AST or ALT lab value that is greater than or equal to 3 X the upper limit of normal and an elevated total bilirubin lab value that is greater than or equal to 2 X the upper limit of normal and, at the same time, an alkaline phosphatase lab value that is less than 2 X the upper limit of normal, as determined by way of protocol-specified laboratory testing or unscheduled laboratory testing. NOTE: Patients will be discontinued from study therapy but followed for safety until the abnormal value(s) has/have normalized, stabilized, or returned to baseline.
- Development of nephrotoxicity, which in the opinion of the investigator, warrants discontinuation of study therapy.

**Protocol/Amendment No.:** 064-02

• Requirement for treatment with an investigational drug.

If a patient discontinues from study therapy for any reason, evaluations (e.g., cultures, radiographic studies) should be performed as clinically indicated at that time. An efficacy assessment of response to study therapy should be documented at the time of study therapy discontinuation. Unless the patient is also withdrawing from the study, the patient should be followed for safety and for the efficacy endpoint through the end of the follow-up period.

Withdrawal from study should be considered for the following reason(s):

• The patient's parent (or guardian) refuses further treatment or follow-up and withdraws consent.

If a patient discontinues/withdraws from the study for any reason, an efficacy assessment of response to study should be documented at the time of study discontinuation/withdrawal.

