- e The blood cultures or cultures from the non-blood site(s), which confirm the evidence of invasive *Candida* infection during the screening phase, must be obtained within 96 hours prior to study entry.
- f Follow-up culture samples to be collected from the site(s) of *Candida* infection, as clinically indicated (see Section 3.2, Study Procedures). Specifically, follow-up CSF cultures should be collected until negative follow-up CSF cultures are documented.
- g When appropriate, a radiographic study from the site of infection (e.g., echocardiogram, chest/abdominal ultrasound) should be performed within 96 hours prior to study entry.
- h Follow-up radiographs are to be performed from the site(s) of infection (e.g., echocardiogram, chest/abdominal ultrasound, CT, MRI) as clinically indicated, based on the site of infection (see Section 3.2, Study Procedures). If a radiographic study that helped confirm the diagnosis of invasive candidiasis is deemed necessary to assess the outcome of study therapy, a follow-up radiographic study must be obtained within 72 hours (3 days) prior to completion of study therapy.
- i The first laboratory safety sample following initiation of study therapy should be performed on Day 4. If collection of a Day 4 sample is not possible, the laboratory sample may be obtained on Day 3 or Day 5 of study therapy. The selected chemistry and hematology laboratory tests for safety are included in Appendix 6.1.
- j Three blood samples (350 μL each) are to be collected on either Day 4 or Day 7 (according to the assigned schedule as described in Section 3.3.2). Plasma will be separated from blood and sent to a central laboratory for pharmacokinetic testing. If sampling cannot be performed on the assigned day, blood samples can be drawn at comparable timepoints on the following day. If a patient undergoes any procedure at baseline or during study therapy that involves collecting CSF, a CSF sample (350 μL) should be retained at each timepoint and sent to a central laboratory for pharmacokinetic testing.

Confidential 27-Aug-2013

**Protocol/Amendment No.:** 064-02

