# Liver Enzyme Abnormalities

Safety assessments of injury or damage to the liver will be performed by monitoring of liver function tests during and at the end of study therapy. Laboratory tests should be repeated if AST or ALT increase to ≥2 times the baseline value. If on repeated measures, the laboratory test elevated at study entry continues to rise (and reaches 6 times the upper limit of normal), study therapy should be discontinued as described in Section 3.2.3.7.1. However, if the enzyme elevations are clearly due to another etiology, the case may be discussed with the SPONSOR Clinical Monitor (or designee) prior to discontinuing the patient from study therapy. If liver enzymes return to normal, rechallenge with the study therapy may be allowed. The decision will be made by the investigator in consultation with the SPONSOR Clinical Monitor (or designee).

Any elevated AST or ALT lab value that is greater than or equal to 3 X the upper limit of normal and an elevated total bilirubin lab value that is greater than or equal to 2 X the upper limit of normal and, at the same time, an alkaline phosphatase lab value that is less than 2 X the upper limit of normal, as determined by way of protocol-specified laboratory testing or unscheduled laboratory testing will be evaluated. The trial site guidance for assessment and follow up of these criteria can be found in the Administrative Binder.

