# 3.4.5.2 Selected Nonserious Adverse Experiences

Events of clinical interest for this trial include:

An elevated AST or ALT lab value that is greater than or equal to 3X the upper limit of normal and an elevated total bilirubin lab value that is greater than or equal to 2X the upper limit of normal and, at the same time, an alkaline phosphatase lab value that is less than 2X the upper limit of normal, as determined by way of protocol-specified laboratory testing or unscheduled laboratory testing.\*

\*NOTE: These criteria are based upon available regulatory guidance documents. The purpose of the criteria is to specify a threshold of abnormal hepatic tests that may require an additional evaluation for an underlying etiology. The trial site guidance for assessment and follow up of these criteria can be found in the Administrative Binder.

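### The hepatic stopping, evaluation and event-of-clinical-interest criterion needs alkaline phosphatase, which the Appendix 6.1 panel omits, so scheduled testing alone cannot show that it is met

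*Combined protocol and SAP*

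**What the plan says.** The same liver criterion appears three times in the protocol: as a reason to discontinue study therapy (Section 3.2.3.7.1), as a trigger for evaluation (Section 3.4.2, Liver Enzyme Abnormalities) and as an event of clinical interest (Section 3.4.5.2). It joins three conditions: AST or ALT at least 3 times ULN, total bilirubin at least 2 times ULN, and a concurrent alkaline phosphatase result "that is less than 2 X the upper limit of normal, as determined by way of protocol-specified laboratory testing or unscheduled laboratory testing". The timing is explicit in the words "at the same time, an alkaline phosphatase lab value". Section 3.4.5.2 repeats the last condition as "an alkaline phosphatase lab value that is less than 2X the upper limit of normal".

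The scheduled safety tests are defined by cross-reference. A footnote to the flow chart in Section 1.7 states: "The selected chemistry and hematology laboratory tests for safety are included in Appendix 6.1". The screening, on-therapy and posttherapy procedures (Sections 3.2.3.3, 3.2.3.5.1 and 3.2.3.5.2) point to the same appendix. Appendix 6.1 lists five hematology tests and seven chemistry tests. The chemistry tests are ALT, AST, urea nitrogen (or urea), creatinine, potassium, direct bilirubin and total bilirubin. Alkaline phosphatase is not listed.

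**The concern.** The criterion names protocol-specified testing as one of two routes by which it is determined, but the protocol-specified panel lacks one of the analytes the criterion needs. It is the only discontinuation reason in Section 3.2.3.7.1 with numeric laboratory thresholds; the other laboratory-related reasons there rest on the investigator's judgment.

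If a scheduled draw meets the transaminase and bilirubin parts, the rule stays open until alkaline phosphatase is also known for the same time. Whether that value exists then depends on what the site chose to order. Safety samples are tested locally, so both the stopping rule and the capture of the event of clinical interest could vary with site practice.

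The protocol itself treats the analyte as relevant. Section 3.1 gives increased alkaline phosphatase as a drug-related adverse experience in 5.2% of the integrated caspofungin safety population, and Section 3.1.1 with Table 3-3 counts raised alkaline phosphatase as a sign of hepatotoxicity with amphotericin B deoxycholate.

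**Working it through.** The plan gives no figure to reproduce here. The check sets each part of the criterion against the scheduled panel.

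**Inputs.** The criterion comes from Sections 3.2.3.7.1, 3.4.2 and 3.4.5.2. The panel and its schedule come from Appendix 6.1.

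| Condition | Analyte | In Appendix 6.1? |
|---|---|---|
| A: AST or ALT ≥ 3 × ULN | AST, ALT | Yes, both |
| B: total bilirubin ≥ 2 × ULN | Total bilirubin | Yes |
| C: alkaline phosphatase < 2 × ULN, concurrent | Alkaline phosphatase | No |

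**Count.** The panel has 5 + 7 = 12 tests, and alkaline phosphatase is 0 of the 12. The panel supplies 2 of the 3 conditions, or 3 of the 4 analytes.

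**Logic.** The criterion is met only if A, B and C all hold.

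- If A or B fails on a scheduled draw, the criterion is not met, and the panel is enough to say so.
- If A and B both hold, the criterion is met exactly when C holds. The panel says nothing about C, so the status is undetermined.

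Scheduled results can therefore return only two answers, not met or undetermined. They cannot return met.

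**Schedule.** Appendix 6.1 applies at screening, Day 4 (± 1 day), Day 7, twice weekly thereafter on therapy, the last day of therapy and 2 weeks after therapy. Alkaline phosphatase is scheduled at none of these. A baseline value is therefore also absent, but this is a side point because condition C is set against ULN and not against baseline.

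**Other routes to the test.** The flow chart, the screening, treatment and follow-up procedures, and the safety-measurement sections contain no other scheduled alkaline phosphatase test. Section 3.4.2 has a repeat-testing instruction, "Laboratory tests should be repeated if AST or ALT increase to" at least twice baseline, but it does not name alkaline phosphatase. That leaves unscheduled testing, which the criterion permits and no available text requires.

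**Source check.** Appendix 6.1 shows no redaction or gap marker, so there is no sign that the test was lost in the public copy.

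**The case against.** The strongest reply is that the text does not strictly contradict itself. The criterion accepts unscheduled testing, Appendix 6.1 describes selected tests, and nothing forbids a site from adding another. The protocol never says that scheduled testing alone must establish the criterion. This is correct, and it confines the point to what scheduled testing can show. It does not remove the gap, because permission to order a test is not an instruction to order it.

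A second reply is that the instruction may sit elsewhere. Section 3.4.2 says: "The trial site guidance for assessment and follow up of these criteria can be found in the Administrative Binder". That guidance was not available and may ask for alkaline phosphatase. If it does, the practical gap is smaller, but the protocol's own panel would still lack an analyte that its own criterion uses.

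A third reply is that patients are still watched. The transaminases and bilirubin are scheduled, so an infant who meets the first two parts is visible to the investigator. Section 3.2.3.7.1 separately covers a "clinically significant laboratory change or abnormality that, in the judgment of the investigator, warrants withdrawal of the patient" from study therapy, and Section 3.4.2 provides for stopping for possibly drug-related events when interruption is clinically indicated. Section 3.4.2 also has a rule on scheduled analytes, which applies after repeat testing: "the laboratory test elevated at study entry continues to rise (and reaches 6 times the upper limit of normal), study therapy should be discontinued". These provisions do limit the consequence. The last is narrower than it looks: it is worded for a test already raised at study entry, allows discussion with the Clinical Monitor if another cause is clear, and refers to Section 3.2.3.7.1, whose list contains no item at 6 times ULN. None of the three provisions makes the separate three-part criterion assessable.

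**Conclusion.** The point holds. Scheduled testing supplies 2 of the 3 conditions of the hepatic criterion and cannot show that it is met in any of its three uses. The omission from Appendix 6.1 is certain on the face of the document. How often a case would stay undetermined in practice is not known: it depends on the unseen site guidance and on local ordering habits, and the documents give no basis for estimating the number of patients affected.

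The consequence is for safety ascertainment and for consistent application of a stated rule. Other stopping provisions remain, and the primary endpoint, the analysis populations and the power are not affected. It should be fixed, but it does not threaten the trial's main inference.

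**What to change.** Reconcile Appendix 6.1 with Sections 3.2.3.7.1, 3.4.2 and 3.4.5.2 so that the scheduled panel and the criterion use the same analytes, and check that the Administrative Binder guidance agrees with the result. No view is offered on which text should change or on which clinical rule or threshold is right.

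The cost is a small amendment. If the criterion text changes, it is wording only. If the panel changes, slightly more sample volume might be needed in very small infants; this is an assumption, as the documents give no volume for the safety samples.
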